## **2 Trial Objectives**

### **2.1 Primary Objective**

To evaluate the tolerability of SGI-110 when administered subcutaneously to Japanese patients with AML

Secondary objectives:

- To perform PK evaluation of plasma SGI-110 and decitabine
- To evaluate efficacy (complete remission rate, composite complete remission rate, overall remission rate, overall survival, composite complete remission duration)
- To evaluate safety through observed AEs and examinations

Exploratory objective:

To perform PD evaluation of the extent of DNA hypomethylation

### **3 Trial Plan**

#### **3.1 Trial Design**

This is a phase 1, multicenter, open-label study to evaluate the tolerability of SGI-110 in Japanese patients with relapsed or refractory AML after undergoing standard therapy or Japanese patients with AML aged 65 years or older who are not eligible for standard chemotherapy.

This trial consists of a screening period, DLT evaluation period, and withdrawal examination. Subjects who complete IMP administration and all observations during the DLT evaluation period, and who do not have any apparent progression of AML, will be permitted to continue treatment with IMP following the DLT evaluation period if they wish. The primary evaluation data for Cohorts 1, 2, and 4 will have a cutoff date of 31 May 2016 and the data for Cohort 3 will have a cutoff date of 30 Nov 2017. The period up until the data cutoff will be defined as the primary evaluation part. This will be followed by an extended treatment part to assess long-term safety, which will include those subjects on IMP treatment who have consented to participate in the extended treatment part. Transition from the primary evaluation part to the extended treatment part will take place at the start of the next course after the data cutoff.

Administration of the IMP will be started in Cohort 1 (36 mg/m^2 in 5-day regimen) and 3 subjects will receive the IMP in this cohort. If none of the 3 subjects has a DLT during the DLT evaluation period, the study will proceed to the next cohort. If one of the 3 subjects experiences a DLT, 3 additional subjects will be enrolled and DLTs will be evaluated in a total of 6 subjects. The study will proceed to the next cohort only if no more than one of the 6 subjects has a DLT. If the number of subjects exhibiting a DLT within a cohort is  $\geq 2/3$  or  $\geq 2/6$ , there will be no dose escalation.

In Cohort 2 (60 mg/m^2 in 5-day regimen) and Cohort 4 (90 mg/m^2 in 5-day regimen), DLTs will be assessed in the same manner. However, even if none of the first 3 subjects enrolled has a DLT, a total of 6 subjects will be enrolled in each of Cohorts 2 and 3 of which the dose has been determined as the recommended dose for a next phase study.

Based on the occurrence of DLTs, the tolerability at the recommended dose for a next phase study will be confirmed in Japanese subjects as well.

The sponsor will review safety data obtained from the previous cohort(s) and judge the transition to the next cohort, including selection of a cohort to proceed to, based on the advice of the Independent Data Monitoring Committee.

If the number of subjects exhibiting DLT within a cohort is  $\geq 2/3$  or  $\geq 2/6$ , then there will be no transition to the next cohort, and the MTD will be determined as follows:

$\geq 2/3$ or $\geq 2/6$ subjects with DLT	MTD
In Cohort 1	$< 36 \text{ mg/m}^2$ in 5-day regimen
In Cohort 2	$36 \text{ mg/m}^2$ in 5-day regimen
In Cohort 4	$60 \text{ mg/m}^2$ in 5-day regimen

If the incidence of DLT does not reach either  $\geq 2/3$  or  $\geq 2/6$  in any of the cohorts in the table above, the MTD will not be determined in this study. For Cohort 3 ( $60 \text{ mg/m}^2$  in 10-day regimen), DLT will be evaluated but the MTD of 10-day regimen will not be determined from the incidence of DLT.

The DLT evaluation period will be from the start of administration in Course 1 to the examination scheduled for Day 29 of Course 1. However, for subjects who have postponed the start of IMP administration scheduled for Day 1 of Course 2 (extended treatment period), the DLT evaluation period will last until the start of IMP administration in Course 2.

Subjects will be hospitalized for treatment during Course 1. Subjects will be required to remain hospitalized until the examination scheduled for Day 29 of Course 1 if they complete the trial in Course 1 (until the withdrawal examination if they are withdrawn during Course 1) and until the start of IMP administration in Course 2 if they proceed to the extended treatment period of Course 2 and the subsequent courses.

Dose-limiting toxicity shall be defined as any of the following AEs occurring during Course 1 for which there is a reasonable probability or possibility of a causal relationship with the IMP (being related to the IMP) if it cannot be reasonably explained by underlying disease, intercurrent illness, or concomitant medications. The severity of AEs will be graded in accordance with Common Terminology Criteria for Adverse Events (CTCAE) version 4.0.

- Non-hematologic toxicity of Grade 3 or higher, except for the following:
  - Nausea, vomiting, or diarrhea of Grade 3 that is controllable by optimal therapy
  - Grade 3 laboratory findings other than serum creatinine (Cr), bilirubin, aspartate aminotransferase (AST), or alanine aminotransferase (ALT), that are not associated with clinical manifestations
- Grade 4 thrombocytopenia that was not present at study entry and that is not resolved within 7 days
- Grade 4 neutropenia that was not present at study entry and that is not resolved within 7 days

- Febrile neutropenia Note

If the febrile neutropenia is not resolved or improved during the DLT evaluation period, it shall be defined as DLT. If the febrile neutropenia is resolved or improved during the DLT evaluation period, it shall be judged whether it is defined as DLT based on the background of the subject and through consultation with the Independent Data Monitoring Committee.

- Any AE that results in a delay of > 4 weeks in starting the next treatment course

Note In this trial, febrile neutropenia is defined as a neutrophil count of < 500/ $\mu$ L accompanied by a fever of  $\geq 38^{\circ}\text{C}$

The DLT evaluation period will be for the duration of Course 1. Subjects who complete IMP administration and all observations during the DLT evaluation period, and who do not have any apparent progression of AML, will be permitted to continue treatment with IMP following the DLT evaluation period if they wish.

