### 3.4 Target Number of Patients

Maximum: 24 subjects

Cohort 1 (36 mg/m^2, 5 days): 3 to 6 subjects

Cohort 2 (60 mg/m^2, 5 days): 3 to 6 subjects

Cohort 3 (60 mg/m^2, 10 days [ie, 5-day administration twice, with a non-dosing period in-between]): 6 subjects

Cohort 4 (90 mg/m^2, 5 days): 3 to 6 subjects

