### 3.5 Rules to Be Observed for Enrollment and Treatment

- 1) The dose or regimen should remain unchanged for each subject, and no subject should be re-enrolled.
- 2) In order to avoid occurrence of unexpected serious adverse drug reactions in multiple subjects, the IMP should be administered to the second subject after the following day of Day 1 of Course 1 in the first subject at each dose level.
- 3) When the administration or examination scheduled for Course 1 cannot be implemented for reasons other than safety, the subject should be excluded from the DLT evaluation, and another subject should be enrolled.
- 4) Administration of SGI-110 is expected to cause myelosuppression and infection (eg, febrile neutropenia, pneumonia, and sepsis). Delay or discontinuation of administration should be determined for subjects who have experienced or are suspected to have experienced pyrexia or infection based on data from laboratory tests, physical examination (body temperature), and imaging tests before the start of the next course and continuing the treatment.
- 5) In and after Course 2 (extended treatment period), IMP administration may be suspended (skipped) from Day 2 and onwards at the discretion of the investigator or subinvestigator, depending on the subject's condition. Subjects who fall under any of the discontinuation criteria should be withdrawn from the trial.

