### **11.3 Analysis Items and Method**

#### **11.3.1 Safety Analysis**

##### **11.3.1.1 Primary Endpoint**

- 1) Definition  
DLT
- 2) Analysis set  
DLT analysis set

3) Analysis method

Dose-limiting toxicities (by preferred term [PT]) occurring during Course 1 in each cohort will be tabulated (number and percentage of subjects with DLTs).

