### **11.5 Rationale for Target Number of Patients**

For Cohorts 1, 2, and 4, tolerability will be evaluated in at least 3 subjects per cohort based on the Guidelines for Clinical Evaluation of Antimalignant Tumor Drugs. If DLTs are evaluated in 3 subjects in a cohort for the recommended dose and regimen, additional subjects will be enrolled for further safety evaluation in 6 subjects. For Cohort 3, tolerability will be evaluated in 6 subjects.

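### Neither document says what two or more DLTs would mean in Cohort 3 (60 mg/m² for 10 days), either for enrolling subjects 4 to 6 or for the tolerability conclusion

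*Protocol*

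**What the plan says.** Protocol Section 3.1 writes the stepwise 3-then-6 assessment for Cohort 1 and extends it to Cohorts 2 and 4. When a cohort reaches 2 or more DLTs in 3 or in 6 subjects, "then there will be no transition to the next cohort, and the MTD will be determined as follows". The MTD table that follows lists Cohorts 1, 2 and 4 only. For Cohort 3, "DLT will be evaluated but the MTD of 10-day regimen will not be determined from the incidence of DLT". SAP Section 3 repeats this design text.

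On size, Section 3.1 provides that, even with no DLT in the first three, "a total of 6 subjects will be enrolled in each of Cohorts 2 and 3". Section 3.4 gives Cohorts 1, 2 and 4 a range of 3 to 6 but Cohort 3 a flat 6. Section 11.5 agrees: "For Cohort 3, tolerability will be evaluated in 6 subjects".

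On pacing, Section 3.5 separates only the first two subjects: "the IMP should be administered to the second subject after the following day of Day 1 of Course 1 in the first subject".

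On the conclusion, Section 3.1 says that, on the basis of the DLTs, "the tolerability at the recommended dose for a next phase study will be confirmed in Japanese subjects as well", and it counts Cohort 3's dose as a recommended dose. The primary analysis (Section 11.3.1.1) is that DLTs "occurring during Course 1 in each cohort will be tabulated (number and percentage of subjects with DLTs". SAP Section 9.2 is also a tabulation.

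**The concern.** Cohort 3 was reinstated so that the 10-day regimen could be assessed in Japanese patients before Study SGI-110-06 started in Japan (Section 1.2.3). DLT is the primary endpoint, and Cohort 3 carries the largest dose per course in the trial. Yet the one numerical safety limit in the protocol has no working consequence there.

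Two things are at stake. The first is exposure: nothing written makes subjects 4 to 6 wait for the first three, or holds them back if two of those three have DLTs. The second is interpretation: the trial is open-label and no count is tied to the word *confirmed*, so what counts as tolerable can be settled after the DLTs are known.

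**Working it through.** **1. The plan's own figure.** The maximum sample size is 6 + 6 + 6 + 6 = 24, as Section 3.4 states. Cohort 3 contributes a fixed 6 to it.

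**2. Does either effect of the limit reach Cohort 3?**
- *No transition or escalation.* Section 15 ends the primary part of Cohorts 1, 2 and 4 on 31 May 2016. Section 1.2.3 dates the reinstatement of Cohort 3 to 05 Sep 2016. Cohort 3 therefore runs last, and there is no transition to block.
- *MTD entry.* This is expressly switched off. That is reasonable in itself, because only one 10-day dose is tested.

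**3. Which outcomes in the first three subjects are covered?** Zero DLTs is covered by the Section 3.1 exception. One DLT is consistent with the fixed size of 6. Two or three DLTs are not addressed. With no stop written and a target of 6, a literal reading leads on to 6.

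**4. What can subjects 4 to 6 change?** If the first three have 2 or more DLTs, the count after six is at least 2. Hence P(at least 2 of 6, given at least 2 of the first 3) = 1, with no assumption needed. The cohort cannot return within the limit.

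**5. Dose per course (mg/m²).** Cohort 1: 36 × 5 = 180. Cohort 2: 60 × 5 = 300. Cohort 4: 90 × 5 = 450. Cohort 3: 60 × 10 = 600.

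**6. How likely is it?** Neither document gives a DLT rate for the 10-day regimen, so p is assumed to lie between 10% and 30%, with subjects independent.
- P(at least 2 of 3) = 3p²(1 − p) + p³
- P(at least 2 of 6) = 1 − (1 − p)⁶ − 6p(1 − p)⁵
- Expected subjects enrolled after the limit is reached = 3 × P(at least 2 of 3)

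| Assumed p | P(≥2 of 3) | Expected extra subjects | P(≥2 of 6) |
|---|---|---|---|
| 10% | 0.027 + 0.001 = 0.028 | 0.08 | 1 − 0.531 − 0.354 = 0.114 |
| 20% | 0.096 + 0.008 = 0.104 | 0.31 | 1 − 0.262 − 0.393 = 0.345 |
| 30% | 0.189 + 0.027 = 0.216 | 0.65 | 1 − 0.118 − 0.303 = 0.580 (unrounded terms) |

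**7. Where does p plausibly lie?** Sections 1.2.2.1.1.1 and 6.1 report no DLT in AML subjects in SGI-110-01 at up to 125 mg/m² for 5 days, which is 125 × 5 = 625 mg/m² per course. Two of 3 MDS subjects at that dose had DLTs. The schedule differs from Cohort 3's, so neither result gives a 10-day rate, but the AML result points towards the low end.

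**8. Is there time to act?** SAP Section 1 cites protocol version 8 of 13 Oct 2017, and the Cohort 3 cutoff is 30 Nov 2017. For Day 29 to fall by the cutoff, Course 1 must start by 30 Nov − 28 days = 02 Nov. Using the Day 26 window it must start by 30 Nov − 25 days = 05 Nov. That leaves 20 to 23 days after version 8.

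**The case against.** The best defence is that the documents are silent here rather than wrong. The limit is worded for any cohort. The exception that takes Cohort 3 to six subjects is written for the case of no DLTs, which implies that someone looks at the first three, and a target of six is not an order to continue despite toxicity. This stands. A reader might infer that the protocol directs enrolment to continue after 2 of 3, but no sentence says so. The gap is a missing consequence combined with a fixed size.

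A reader might also infer that DLTs have no bearing on the tolerability conclusion. The text does not support that either. Section 3.1 and SAP Section 3 tie the conclusion to the DLTs, and only the threshold is missing.

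The synopsis has the sponsor confirm DLT incidence in each cohort, with IDMC advice. That narrows the gap without closing it, because the stated action is again transition to the next cohort. Other safeguards are real: hospitalization throughout Course 1 (7.1.4.2.1), prompt DLT reporting (8.2.2), IDMC consultation on resolved febrile neutropenia (3.1), individual withdrawal criteria (9.2) and sponsor termination (13.8.2). They protect individuals or are discretionary, and none is tied to a cohort DLT count.

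Finally, a single-regimen cohort can reasonably be descriptive, and several passages (3.2, 11.5, SAP 12) say only that tolerability will be *evaluated*. That would answer the point about interpretation if Section 3.1 and SAP Section 3 did not also say *confirmed*. It does not answer the point about enrolment.

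**Conclusion.** The point holds as an unstated consequence. For Cohort 3 neither document says what 2 or more DLTs would do to enrolment or to the tolerability conclusion. The part that needs no assumption is that, after 2 DLTs in the first three, three more subjects treated at 600 mg/m² per course cannot bring the count back within the protocol's own limit.

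The likely size is modest. The chance of that situation is 3% to 22% at assumed DLT rates of 10% to 30%, or 0.08 to 0.65 extra subjects on average. These figures rest on assumed rates and independent subjects. Rates of 40% or 50% would look far worse, but nothing in the documents supports them, and the absence of DLTs in AML subjects in SGI-110-01 points the other way. The point deserves a change because it concerns the primary endpoint at the trial's highest dose per course and the remedy is cheap. The pause may come late: few enrolment days remained after version 8.

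**What to change.** Add to Protocol Section 3.1 and SAP Sections 3 and 9.2 that the existing limit applies to Cohort 3 for tolerability, without naming an MTD:
- 2 or more DLTs among the first three subjects pauses further enrolment pending IDMC advice.
- 2 or more DLTs in six means tolerability is not described as confirmed.

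Record the date of this decision relative to the DLT data already seen. If enrolment is complete and the DLT data are known, add no criterion after the fact. Report the Cohort 3 DLT count and describe tolerability as *evaluated*, not *confirmed*. An exact confidence interval on six subjects would not substitute for the rule, because it does not supply the missing stop.

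The cost is wording, a possible pause in enrolment, and a less favourable statement if the limit is reached. Since 2 or more in the first three is contained in 2 or more in six, the chance of reaching the limit is the last column of the table: 11%, 34% and 58% at assumed rates of 10%, 20% and 30%. No extra subjects or data are needed, and the maximum of 24 is unchanged.

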### **3.2 Rationale for Trial Design**

In the trial, the dose escalation was planned with consideration of the subjects' safety and based on the "Guidelines for Clinical Evaluation of Antimalignant Tumor Drugs (Notification No. 1101001 of the Evaluation and Licensing Division, Pharmaceutical and Food Safety Bureau dated 01 Nov 2005)."

As mentioned in [Section 1.2.3](#) Trial Rationale, the doses and regimen were chosen based on evaluations of the safety, efficacy, and PD of SGI-110 in a clinical trial conducted outside of Japan (Study SGI-110-01), and it has been decided to adopt a study design to evaluate the tolerability in each cohort and gradually escalate the dose.

Since results of Study SGI-110-01 suggest that the recommended dose for non-Japanese patients is assumed to be 60 mg/m^2, the primary dose to be investigated has been set as 60 mg/m^2. This study is the first clinical trial of SGI-110 involving Japanese patients with AML and, therefore, in considering the subjects' safety, the initial dose will be 36 mg/m^2, which was one of the doses used in Study SGI-110-01 and is a lower dose than the primary dose of 60 mg/m^2. The maximum dose will be 90 mg/m^2, which was determined to be the MTD in Study SGI-110-01 and is suggested to be effective according to exploratory evaluation. In addition, the tolerability of SGI-110 at 60 mg/m^2 once daily for 10 days will be evaluated in Japanese patients in this study because the same dose and regimen is planned to be adopted in Study SGI-110-06 in patients with relapsed or refractory AML.

As mentioned in [Section 1.2.2](#) Clinical Study Results, occurrences of myelosuppression and decreased blood cell counts, and infections attributable to these, as well as

occurrences of digestive symptoms are anticipated following administration of SGI-110. Therefore subjects will be hospitalized during Course 1, when the IMP will be administered for the first time to them, so they can be carefully monitored. Thereafter, the subjects are to visit the trial site at least once weekly to undergo hematological tests for evaluation of decreased blood cell counts and to undergo a medical examination by a physician to check their general condition. In addition, a chest X-ray examination and blood biochemistry test are to be performed before the start of the next course in order to ensure the subjects' safety.

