**7.1.4.1.3 Day 8, Day 15, and Day 22 of Course 1**

The observations, examinations, and evaluations listed below will be conducted, and the dates of the conduct and data obtained will be documented in the medical records and CRF.

Clinical Symptoms	Subjective symptoms and objective findings
Vital Signs	Blood pressure (systolic/diastolic), pulse rate, and body temperature
Hematology Test	Hb, Hct, RBC count, WBC count, differential WBC count (visual count: blast cells [leukemia cells], lymphoblastoid cells, monoblasts, promyelocytes, myelocytes, metamyelocytes, segmented neutrophils, stab leucocytes, lymphocytes, eosinophils, monocytes, basophils, prolymphocytes, and promonocytes), platelet count, and reticulocytes
PD evaluation	Blood sampling

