**7.1.4.1.4 Day 29 of Course 1**

The observations, examinations, and evaluations listed below will be conducted, and the dates of the conduct and data obtained will be documented in the medical records and CRF.

Clinical Symptoms	Subjective symptoms and objective findings
Pregnancy Test a	Urinary or serum HCG
Vital Signs	Blood pressure (systolic/diastolic), pulse rate, and body temperature
Body Weight	Body weight
Twelve-lead ECG and chest X-ray	Twelve-lead ECG and chest X-ray

Hematology Test	Hb, Hct, RBC count, WBC count, differential WBC count (visual count: blast cells [leukemia cells], lymphoblastoid cells, monoblasts, promyelocytes, myelocytes, metamyelocytes, segmented neutrophils, stab leucocytes, lymphocytes, eosinophils, monocytes, basophils, prolymphocytes, and promonocytes), platelet count, and reticulocytes
Blood Biochemistry Test	AST (GOT), ALT (GPT), ALP, LDH, TP, ALB, T-Bil, BUN, UA, Cr, blood glucose (fasting), Ca, Mg, Na, K, and Cl
Urinalysis	Bilirubin, occult blood, protein, and urobilinogen
General Condition	ECOG PS
Bone Marrow Aspiration	Percentage of bone marrow fluid (blasts, lymphoblasts, monoblasts, promyelocytes, myelocytes, metamyelocytes, segmented neutrophils, stab leucocytes, lymphocytes, eosinophils, monocytes, basophils, normoblasts, pronormoblasts, erythroblasts, plasma cells, and megakaryocytes), M/E ratio, and cellularity
PD Evaluation	Blood sampling

HCG = Human chorionic gonadotropin

a A pregnancy test will be performed in female subjects at the trial site. However, a pregnancy test is not required for subjects who have undergone bilateral oophorectomy or hysterectomy, or subjects who have been amenorrheic without a medical cause for at least 12 consecutive months.

Prior to transition to Course 2 and subsequent courses, written informed consent (using written information for subjects) to extended treatment in Course 2 and subsequent courses will be obtained from subjects who wish to continue to receive the treatment and are eligible for extended treatment in the opinion of the investigator or subinvestigator (between Day 22 of Course 1 and the start of Course 2). In principle, each course should consist of 28 days, and if the examination scheduled for Day 29 is performed between Day 26 and Day 28 for example, which is within the acceptable window, IMP administration for the next course should be started on or after Day 29 of the current course.

#### 7.1.4.1.5 Day 1 of Course 2

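### The Course 1 chemistry schedule does not ensure that transient, symptom-free Grade 3 creatinine, bilirubin, AST or ALT DLTs are detected

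*Protocol*

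**What the plan says.** Protocol 3.1, repeated in SAP 3, lists as a DLT "Non-hematologic toxicity of Grade 3 or higher, except for the following", provided the event is judged related to the drug and not otherwise explained. One exception is "Grade 3 laboratory findings other than serum creatinine (Cr), bilirubin, aspartate aminotransferase (AST), or alanine aminotransferase (ALT), that are not associated with clinical manifestations". The four named analytes fall outside that exception. No duration is attached to them, unlike the cytopenia criteria, for example "Grade 4 neutropenia that was not present at study entry and that is not resolved within 7 days".

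On timing, "The DLT evaluation period will be from the start of administration in Course 1 to the examination scheduled for Day 29 of Course 1". If Course 2 is postponed, "the DLT evaluation period will last until the start of IMP administration in Course 2".

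The chemistry panel appears on Day 1 before dosing (7.1.4.1.1 and 7.1.4.2.1; results up to 4 days old may be used) and again on Day 29 (7.1.4.1.4 and 7.1.4.2.4): "AST (GOT), ALT (GPT), ALP, LDH, TP, ALB, T-Bil, BUN, UA, Cr, blood glucose (fasting), Ca, Mg, Na, K, and Cl". The entries for "Day 8, Day 15, and Day 22 of Course 1" (7.1.4.1.3, and 7.1.4.2.3 for Cohort 3) require blood for hematology and PD but no chemistry. Neither Days 2 to 5 nor, in Cohort 3, Days 9 to 12 include chemistry. Protocol 3.2 explains the later panel as a safety check: "a chest X-ray examination and blood biochemistry test are to be performed before the start of the next course".

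The DLT analysis set (Protocol 11.1.1.1, SAP 5.1.1.1) admits subjects who received all doses and completed the assessments that were scheduled.

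**The concern.** The endpoint definition and the measurement schedule do not match. The definition counts a laboratory event that may cause no symptoms, while the schedule looks for it only at the end of the period. A subject with no mid-course chemistry still counts as fully evaluable and, unless something else prompted a test, as free of these DLTs. The SAP 9.3.3 shift table for the worst grade in each course rests, for Course 1 chemistry, on one scheduled post-dose value.

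DLT is the primary endpoint. It feeds the escalation decision and the MTD in Cohorts 1, 2 and 4, and the tolerability statement for the 10-day regimen in Cohort 3. Missed events can only push these toward tolerable. If sites differ in how often they test inpatients, the observed incidence in cohorts of 3 to 6 also depends on who enrolled the subjects.

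**Working it through.** The plan states no detection rate for laboratory DLTs, so it has no figure of its own to reproduce.

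**Step 1. Scheduled Course 1 chemistry** (Table 7.1-1, 7.1.4.1.1 to 7.1.4.1.4, 7.1.4.2.1 to 7.1.4.2.4)

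| Time | Chemistry | Hematology |
|---|---|---|
| Screening; Day 1 predose | yes | yes |
| Days 2–5 (and 9–12 in Cohort 3) | no | no |
| Days 8, 15, 22 | no | yes |
| Day 29 (window 26–32) | yes | yes |

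Two further panels can fall in the DLT period: the withdrawal examination (7.1.5) and Course 2 Day 1 predose chemistry when Course 2 is postponed. For a subject who completes Course 1, neither falls between Day 2 and Day 25.

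**Step 2. Gap between scheduled panels.** Nominal: 29 − 1 = 28 days. Shortest: 26 − 1 = 25. Longest: (32 − 1) + 4 = 35. Day 29 is 29 − 5 = 24 days after the last dose in Cohorts 1, 2 and 4, and 29 − 12 = 17 days after it in Cohort 3.

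**Step 3. Share of episodes that a scheduled draw meets.** Assumptions, none from the documents: onset is uniform over Days 2 to 29, the abnormality lasts d days, and no unscheduled chemistry is done. A Day 29 draw meets an episode if onset falls on one of the last d of the 28 days, giving d/28. Draws on Days 8, 15, 22 and 29 give min(1, d/7).

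| d (days) | Day 29 only | Days 8, 15, 22, 29 |
|---|---|---|
| 3 | 3/28 = 11% | 3/7 = 43% |
| 7 | 7/28 = 25% | 100% |
| 14 | 14/28 = 50% | 100% |
| 21 | 21/28 = 75% | 100% |

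**Step 4. Sensitivity.**
- Draw date, d = 7: a Day 32 draw meets onsets on Days 26 to 29 only, 4/28 = 14%. A Day 26 draw meets 7 of the 25 possible onset days up to Day 26, 28%.
- Early onset, Days 2 to 8: even an episode starting on Day 8 must last 22 days to reach Day 29, so a Day 29 draw catches none lasting up to 21 days.

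**Step 5. Secondary point, the 7-day cytopenia rule.** Scheduled counts are nominally 7 days apart. A single Grade 4 count between two recovered counts at that spacing fits any duration from 1 to 13 days, on both sides of the limit. An episode of L days (7 < L < 14) is Grade 4 at two nominal visits with probability (L − 7)/7: 1/7 = 14% at 8 days and 3/7 = 43% at 10 days. Visit windows widen this: Day 15 (12–18) to Day 22 (19–25) in Cohorts 1, 2 and 4 can be 19 − 18 = 1 to 25 − 12 = 13 days apart. Cohort 3 is tighter from Day 8 (fixed) to Day 15 (13–18), at 5 to 10 days.

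**The case against.** The strongest reply is that a DLT is an adverse event from any source, not a scheduled value. An abnormal laboratory finding can be an adverse event whenever it is found (Protocol 8.1.1), subjects stay in hospital throughout Course 1 for close monitoring (3.2), adverse events are collected continuously, and SAP 6.3 expects data from unspecified time points. This stands against a stronger claim. A reader might infer that the primary endpoint misses most hepatic and renal DLTs. The documents do not support that, because they do not say how much unscheduled chemistry is done. Even for scheduled testing alone, more than half are missed only if episodes last under 14 days with uniform onset, or longer if onset is early.

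A reader might also put an assumed rate through the 3+3 rule. A true 30% rate of 7-day events, seen as 0.30 × 0.25 = 7.5%, would raise the chance of escalating, (1 − p)³ + 3p(1 − p)⁵, from 0.49 to 0.94. The documents do not support that as a measure of the harm:
- No rate for these events is given. The earlier study's most frequent drug-related events, listed down to 11%, include none in the four analytes, and its DLTs were cytopenias, febrile neutropenia and sepsis (1.2.2.1.1.1, 1.2.2.1.1.2).
- The sum treats these as the only DLTs, yet febrile neutropenia of any cause occurred in 39% to 43% of those subjects.
- Cohort 2 goes to 6 subjects even after 0 of 3, and Cohort 3 sets no MTD.
- The sponsor decides transition on its review of safety data with advice from the monitoring committee, not from counts alone.

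The schedule also has a stated rationale: weekly hematology for the expected myelosuppression, and chemistry before the next course. Fever triggers additional blood tests (6.2.2), which helps with counts, though that section does not name chemistry.

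None of this closes the gap. Hospitalization permits mid-course chemistry; the protocol neither requires it nor sets its timing.

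**Conclusion.** The mismatch is confirmed in all four cohorts. The schedule does not ensure detection of transient, symptom-free Grade 3 creatinine, bilirubin, AST or ALT DLTs. Ascertainment rests on unscheduled testing that varies by site, and DLT incidence may be underestimated. The direction of any bias is clear; its size is not. The capture figures depend on uniform onset, chosen durations and no unscheduled testing, so they compare two schedules and do not estimate events lost in this trial. The cytopenia point is lesser: roughly weekly counts settle the 7-day criterion imprecisely, though they are not uninformative.

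This should be fixed because it touches the primary endpoint and the remedy is cheap. The documents do not show that it has altered an escalation decision.

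**What to change.** - **Cohort 3, prospectively:** in Table 7.1-1 and 7.1.4.2.3, add at least Cr, T-Bil, AST and ALT to the blood already drawn on Days 8, 15 and 22 of Course 1. Make the same change in 7.1.4.1.3 so that the protocol is consistent.
- **Cohorts 1, 2 and 4, retrospectively:** their primary data cutoff (31 May 2016) preceded the amendment that reinstated Cohort 3 (05 Sep 2016), so a new schedule cannot change their Course 1 data. Retrieve local Course 1 chemistry, and report beside the DLT table how many subjects in each cohort had any mid-course value. Do the same for any Cohort 3 subject whose Course 1 is already over; the SAP is written against a protocol version dated 13 Oct 2017, shortly before that cohort's cutoff of 30 Nov 2017.
- **Cytopenia rule:** enter every local blood count from the Course 1 stay in the CRF, so that time to resolution is judged on all available counts.

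The cost is a protocol amendment, three added panels per subject on existing draws, retrieval and CRF entry of local results, and possibly a few more recorded DLTs. No dose or clinical rule changes.
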